To address Aims 2,3,4: Among 210 SO and 315 RA families (i.e., total N=525 families) with 5-12 year-old children, we will examine effects of ADAPT modalities and sequences/timing on multiple behaviors and outcomes (i.e., (i) coercive family interactions, positive parenting, couple adjustment, and co-

parenting, (ii) parents PTSD symptoms, depression symptoms, substance use, (iii) child behavior and emotional problems, and positive adjustment, by conducting a 2-stage SMART, and (iv) document participation, satisfaction, and fidelity. To assess behaviors and outcomes, we will administer and collect a series of assessments (Table 1 appendix) at 4 timepoints.

For Aims 2, 3, and 4, we will use a 2-stage SMART design to examine the optimal sequence, dosage, and delivery formats of ADAPT for active duty military families living in a range of operational tempo contexts. We will recruit a total of 525 families living on three installations: Fort Bragg (North Carolina), Fort Campbell (Kentucky) and Forts Belvoir/Myer, with 210 families recruited from Fort Bragg and Fort Campbell and 105 from Forts Belvoir/Myer.

5.2 Study Procedures:

Subjects for this study include: (I) 525 active duty clinical trial participants recruited from 4 bases who will be randomized to first stage (brief interventions) and second stage (more intensive booster ADAPT programs for families who do not benefit from the first stage interventions); (II) Twelve current study families (N = 24) who will participate in focus groups; (III) 525 children participants between the ages of 5-12 of clinical trial participants who will be asked to participate in assessments only; (IV) Up to 1890 teachers who will be asked to complete the Behavior Assessment System for Children, Second Edition (BASC-3) each yr that the child is in the study (usually 3 grades)

Focus group Participants

We will hold two focus groups with study parents to inform program modifications. Each focus group will consist of 12 participants, one group Special Operations (SO) participants and one group Regular Army (RA) participants, both on Fort Bragg, NC.

Clinical Trial Participants

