Active duty families will be living in a range of operational tempo (OPTEMPO) contexts (i.e., Regular Army/RA and Special Operations/SO) on one of four military installations. All participants will be in units with deployments occurring during the study period. 525 families will be recruited from target bases as follows: (a) Fort Bragg, NC – 210 families recruited, including 105 SO and 105 RA. (b) Forts Belvoir/Myer, VA – 105 Active Duty families recruited. (c) Fort Campbell, KY– 210 families recruited, including 105 SO and 105 RA.

Clinical Trial Participants will be asked to do the following:

- (1) Complete assessments at four time points. Assessments are listed and described below and included on the final page of the protocol.
 - a. T1 (baseline (BL) and prior to the start of the intervention); both on-line and in-home data is collected from families; child self-report measures will be gathered and are standardized with children over 5.
 - b. Responder Checkpoint – Parent Locus of Control 22-item questionnaire completed by parents 4 weeks after they start the intervention

- c. T2 (6 months following baseline); only online parent data will be gathered, (no in-home assessment)
 - d. T3 (12 months following BL, i.e. following the end of the reintegration session(s) and program completion); both on-line and in-home data is collected from families, child self-report measures will be gathered from children over age 5.
 - e. T4 (24 months after BL); both on-line and in-home data is collected from families, child self-report measures will be gathered from children over age 5.
2. Participate in videotaped (with audio) in-home parent-child interaction tasks lasting a total of 30 minutes at three time points (BL/T1, T3, and T4). These interaction tasks are administered and videotaped by trained assessment technicians in the participants' homes. If preferred, participants may complete assessments outside the home at project offices. Video and audio of study participants will be accessed only by the investigators and trained members of the coding team.
3. Fill out online questionnaires at the time of in-home assessments (BL/T1, T3, and T4).

Note: childcare provided by study staff is offered during in-home assessments for siblings. If study staff are not available to provide childcare, a \$30 gift card stipend will be offered to the family so that they can arrange their own childcare.

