a. ADAPT Online. Participants will have access to the full ADAPT website (12 modules, online discussion forum). Participants are directed to the first ADAPT session, and as each session is completed (all materials in a session opened by at least one parent) families receive a personalized congratulations email and continue to the next module. Participants may see the entire program on the ADAPT dashboard; they are encouraged to proceed in the specified order. Each online session consists of a skills video (demonstrating a specific skill), a practice video (modeling how parents practice skills with child(ren)), downloadable summaries of key skills, fillable PDF forms with home practice assignments, a knowledge quiz, and downloadable mindfulness exercises that can be played directly from the ADAPT site as well as from smartphones, tablets, and computers. Participants are compensated at the end of their time period according to the portion of the modules completed. In addition, they are encouraged to respond to the 7 questions prompted by the online facilitator. To encourage this exchange, participants who respond will be entered into a drawing for a \$100 gift card (up to 7 entries). At the end of the online group, one winner will be drawn at random. For example, if there are 10 participants in Cohort 1 and all 10 of them answer each of the 7 facilitator questions then there would be 70 entries for the drawing (10 participants x 7 entries each). This would give each participant a 7% chance that their name would be drawn to receive a \$100 gift card;

b. Condensed group-based ADAPT. Participants will meet for 2 week/weekend days two weeks apart, for 6 hours each day (excluding holidays) at a time convenient to participants. Dinner and childcare are provided. If families are unable to or elect not to register for CYS childcare on the installation or the minimum number of children for CYS childcare is not met, participants will be offered a \$50 stipend in the form of a gift card to arrange their own childcare in order to attend workshop;

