Facilitators who deliver the ADAPT intervention are a combination of U of MN paid staff, U of MN volunteers and military affiliated professionals on those installations who have the required approval for program delivery. Facilitators complete comprehensive face-to-face training prior to starting groups. An extensive training and coaching infrastructure already exists (i.e., training manuals, videotapes, a HIPAA-compliant database for uploading and storage of training and group video material). In our current and past DOD and NIH funded ADAPT studies we have successfully trained over 50 individuals as facilitators. Training will be delivered either on the installation by Drs. [name] and [name] or in Minnesota with prior DOD/MOMRP approval. ADAPT training, which consists of two workshops, and, following workshop training, bi-weekly coaching focused on facilitation of group sessions.

Facilitators are not involved in the randomization or assessment of participants, and it is up to them if they chose to share information about the study with military families in order to assist with recruitment. Facilitators will be told when there is sufficient number of families to begin a workshop and they are given the list of families who will be invited to the workshop. Facilitators plan the workshop logistics with the site study coordinator, including the best day and time to offer the workshops with facilitator schedules, needs of families and space availability in mind. The workshops take place on two full days (6 hours per day, excluding breaks and lunch), two weeks apart (e.g. week 1, week 3 of a month). Two to three facilitators run each workshop. Attendance and end of day evaluations are collected by facilitators and given to the study site coordinator for processing. Between workshops, facilitators contact families by phone once a week to check in and assist with home practice completion, and troubleshoot skills that have been taught. A brief record of this contact is recorded in a secure on-line portal by facilitators for the purposes of coaching.

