17.0 Data Management

17.1 Data Analysis Plan:

Analyses will be conducted in several steps, starting with preliminary and preparatory analyses including data reduction and evaluation of psychometric properties, followed by evaluation of missing data of criterion measures. For the primary efficacy evaluation aims of main effect components and the four adaptive intervention strategies we will employ standard normal theory Analysis of Covariance factorial and fractional factorial analyses to address study aims using pre-post assessment scores for parent and child adjustment constructs. To address the non-independence of subjects in the embedded adaptive intervention designs we will estimate Linear mixed models and weighted least squares regressions for estimation of the embedded adaptive intervention contrasts. Descriptive statistics (mean, range, SD) will be used in reporting participation, satisfaction (for fathers and mothers), and implementation fidelity (for each provider and the group of ADAPT providers).

17.2 Power Analysis:

First, we chose a power convention of .80 with a two-sided alpha level of .05 to reduce the probability of obtaining a false positive improvement or intervention effect rejecting the null when it is true (Type-I error at 5% chance). Second, we powered the study to detect small to medium effect sizes for the first and second stage randomizations. The first stage randomization is allocated with a 1:1 ratio to group conditions as depicted in Figure 6. Based on the ROC analyses we estimate a potential 50% non-response rate for both the online and weekend condensed groups. After the Week 4 assessment of response criteria, non-responders will also be randomized to second stage interventions with a 1:1 allocation.

More specifically, power needed to be estimated by addressing the restricted randomization scheme and appropriate weighting of the overrepresentation of responders and underrepresentation of nonresponders. We employed procedures outlined by Oetting and colleagues for estimating power in SMART trial designs. As recommended, we specified an alpha level of .10 and power of .80. The first main research question (2a) addresses main effects of initial stage randomization,

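### The standard ANCOVA planned for main effects 2a and 2b makes no allowance for shared workshops or booster groups, so any within-group correlation makes its standard errors too small

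*Combined protocol and SAP*

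**What the plan says.** Section 17.1 assigns the main-effect components to "standard normal theory Analysis of Covariance factorial and fractional factorial analyses to address study aims using pre-post assessment scores". Section 17.2 defines 2a as the main effect of the first-stage randomization and 2b as that of the second stage among non-responders.

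The one sentence in 17.1 on dependence begins "To address the non-independence of subjects in the embedded adaptive intervention designs we will estimate Linear mixed models", adds weighted least squares, and states the purpose as "for estimation of the embedded adaptive intervention contrasts". No workshop term, booster-group term, cluster-robust variance, ICC or design effect appears in 17.1 or 17.2.

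Section 5.2 describes the delivery:

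- **Condensed group (one arm of 2a).** "Participants will meet for 2 week/weekend days two weeks apart, for 6 hours each day". Two to three facilitators run each workshop, and "they are given the list of families who will be invited to the workshop". The number of families per workshop is not stated. The other arm is online.
- **Booster group (one arm of 2b).** Three weekly sessions with two facilitators. One place gives about 6 families per group; another allows up to 10 other families, so at most 11. The other arm receives individual sessions.

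The family is the implied unit of analysis, since the sample is counted in families: "Among 210 SO and 315 RA families (i.e., total N=525 families) with 5-12 year-old children".

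**The concern.** In each contrast one arm is treated in groups and the other is not. Group composition, facilitators and discussion can make outcomes of families in the same group more alike. Standard ANCOVA treats all families as independent, so it leaves the between-group component out of the variance of the grouped arm's mean. The sentence on mixed models does not fill the gap. It is confined to the strategy contrasts, where there is a separate reason for dependence: in the section 17.2 table, responder cells A and D each enter two strategies. That overlap does not arise in 2a or 2b.

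Two of the three main questions are affected. With group correlation, their confidence intervals would be too narrow and their Type I error would exceed the stated level. Three limits apply:

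- Workshop correlation does not inflate 2b, because non-responders from one workshop are randomized to both boosters.
- Booster-group correlation reaches 2a only if booster groups are kept separate by first-stage arm.
- Site differences common to both arms inflate neither test.

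**Working it through.** **Inputs from the documents.** N = 473 for 2a and 236 for 2b after 10% attrition; 1:1 allocation at both stages; 50% non-response (all section 17.2); booster groups of about 6, or at most 11 (section 5.2).

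**Assumptions.** ICC of .01 to .10 for the baseline-adjusted outcome, averaged over listed families; 10 analysed families per workshop, with 6 as a low case; no correlation among online families.

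**The plan's own figures.** With MDE = (z_alpha + z_power) × 2/√N, two-sided alpha .05 gives .258 (2a) and .365 (2b), and alpha .10 gives .229 and .324. The table states .324 and .458. These match only at two-sided .10 with the variance doubled (.3234 and .4578). The text does not explain the doubling.

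**True variance divided by ANCOVA variance** (one arm grouped, 1:1):

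- 2a, booster groups mixing the first-stage arms: 1 + (m_w − 1) × ICC/2
- 2a, booster groups separate by arm: add .25 × (m_b − 1) × ICC, since .50 × .50 = .25 of each arm is in booster groups
- 2b: 1 + (m_b − 1) × ICC/2

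True size at nominal .05 is 2Φ(−1.96/√ratio). At ICC .05:

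- 2a, workshops of 10: ratio 1 + 9(.05)/2 = 1.225; √ratio = 1.107; size .077
- 2b, groups of 6: ratio 1 + 5(.05)/2 = 1.125; √ratio = 1.061; size .065

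| True size at nominal .05 | ICC .01 | .02 | .05 | .10 |
|---|---|---|---|---|
| 2a, workshops of 10, boosters mixed | .055 | .060 | .077 | .104 |
| 2a, workshops of 10, boosters of 6 separate by arm | .057 | .063 | .084 | .118 |
| 2a, workshops of 6, boosters mixed | .053 | .056 | .065 | .080 |
| 2b, groups of 6 | .053 | .056 | .065 | .080 |
| 2b, groups of 11 | .056 | .062 | .080 | .110 |

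If 10 and 6 are sizes before the planned 10–20% attrition, (m − 1) is multiplied by .90 to .80, and the ICC .05 figures become .071–.074 (2a, boosters mixed) and .062–.063 (2b). At nominal .10 and ICC .05 they are .137 (2a, boosters mixed) and .121 (2b, groups of 6).

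**Simulation of the planned ANCOVA** (N = 473, baseline covariate, sites 40/40/20 from section 5.2, groups formed within site, workshops of 10, boosters of 6, 12,000 replicates per cell):

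- 2a at ICC .01/.02/.05/.10: .053/.064/.078/.103 with mixed booster groups; .055/.066/.088/.114 with separate groups
- 2b: .061–.063 at ICC .05; .080–.085 at ICC .10
- Workshop correlation alone (ICC .05/.10): 2b stays at .050/.048
- Booster correlation alone, mixed groups (ICC .05/.10): 2a stays at .051/.054
- Site variance alone (.05 or .10): .051 for both tests

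**Effect on power.** At alpha .05 the cluster-adjusted MDE is 2.80 × 2/√N × √ratio. For 2a it is .285 (ICC .05) to .323 (ICC .10, separate booster groups); for 2b it is .387 to .408. These lie below the stated .324 and .458.

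**The case against.** The strongest objection is that the size is assumed. The documents give no ICC and no workshop size, and at ICC .01 to .02 the excess is small. This stands as a limit on magnitude. It does not affect direction, which holds for any positive correlation.

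Attendance is a second point. The calculation applies the ICC to every listed family, and section 5.2 sends families who do not complete the checkpoint questionnaire to boosters, so some listed families may never attend. If each family attends with an assumed probability of 60–80% and only attenders share the group effect, (m − 1) × ICC shrinks by roughly the square of that rate. At ICC .05 the sizes fall to about .059–.067 (2a, workshops of 10) and .055–.059 (2b, groups of 6). This reduction does not apply if the ICC is taken as an average over listed families, as assumed here. In the other direction, booster groups of 11 raise 2b to .080 at ICC .05.

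Third, the online arm may also be clustered: section 5.2 describes a facilitator, a forum and cohorts. Correlation there would add to the problem in 2a, and the partially nested model does not cover it.

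Fourth, the MDE table appears to have slack. The comparison above sets alpha .05 figures against a table that matches only at alpha .10 with doubled variance, so it does not show that the plan allowed for clustering. Slack in power also cannot correct standard errors at the analysis.

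**Conclusion.** The concern holds. The plan gives 2a and 2b a method that ignores group delivery in one arm of each contrast, and no other text supplies the missing term. For workshops of 10 and booster groups of 6 at ICC .05, a nominal .05 test runs at about .077 for 2a (.084 if booster groups are separate by first-stage arm) and .065 for 2b. The ICC, the workshop size and independence of online families are assumptions, so confidence in the size is medium, while the direction is clear whenever the correlation is positive. This should be corrected because the remedy is cheap and two main questions depend on it. It is not a flaw in the design or the sample size.

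**What to change.** In section 17.1, specify for 2a and 2b a family-level analysis with one row per family per outcome, using a baseline-adjusted, partially nested linear mixed model with:

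1. fixed effects for installation;
2. a random intercept for the assigned workshop in 2a and for the assigned booster group in 2b (also in 2a if booster groups are separate by first-stage arm), with no such term for families assigned to none;
3. Satterthwaite or Kenward–Roger degrees of freedom.

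Define the group by the invitation or name list, not by attendance. A family never placed on a list is its own cluster. Cluster-robust variance (CR2, small-sample degrees of freedom) with the same site terms is acceptable for 2b, and for 2a when booster groups mix the arms. Keep workshop and booster-group IDs in the analysis file; an online-cohort ID would be a useful addition. If both parents are ever entered as rows, add a family random intercept. State as limitations that facilitators running several groups and the online forum are not modelled.

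Two texts must be reconciled before coding. Section 4.1 gives a group booster in both strategies 3 and 4, against section 5.2 and the 2b contrast in 17.2. Section 17.2 also states two alpha levels: two-sided .05, and then "As recommended, we specified an alpha level of .10 and power of .80".

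**Performance.** In simulation at ICC .02 to .10, the mixed model held size at .048–.052 (2a) and .049–.051 (2b), and CR2 at .049–.053 and .052–.054. With booster groups separate by arm and two random intercepts, 2a ran at .053 (ICC .05) and .057 (ICC .10; 4,000 replicates). Without the site terms the 2a mixed model is conservative (.042 and .033 at ICC .05 with site variance .05 and .10).

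**Cost.** SAP wording and slightly more modelling; section 5.2 already provides for the lists. If the correlation is real, intervals widen by about 11% (2a, workshops of 10) and 6% (2b, groups of 6) at ICC .05. If the true ICC is zero, the mixed model is slightly conservative (.043 and .045, standard errors about 3% larger), while CR2 costs almost nothing (.048 and .051).

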All measures are listed in the table below and include: (1) The Parenting Locus of Control (PLOC); (2) The Family Interaction Task (FIT); (3) The Alabama Parenting Questionnaire (APQ-22); (4) Deviant Peer Association (PERS); (5) The Behavior Assessment System for Children, Third Edition (BASC-3); (6) Coping with Children's Negative Emotions (CCNES); (7) The UCLA PTSD-Reaction Index (PTSD-RI); (8) the Children's Depression Inventory (CDI); (9) Describing Friends; (10) PTSD Checklist (PCL); (9) Difficulties in Emotion Regulation Scale (DERS); (11) The Five Facet Mindfulness Questionnaire (FFMQ); (12) Receipt of Help (PSI); (13) Alcohol Use Disorders Identification Test (AUDIT); (14) Center for Epidemiologic Studies Depression Scale (CESD); (15) Deployment Risk and Resilience Inventory (DRRI); (16) Differential Ability Scales (DAS-7); (17) Moral Injury (MIES); (18) Parenting Mindfulness (IEM-P); Parenting Identity; (19) NIH Toolbox Flanker (EF – Inhibitory Control); (20) NIH Toolbox Peabody Picture Vocabulary Test; (21) Deviant Peer Association (TPRISK) Process measures include: satisfaction questionnaires, attendance, practice, online use, and coder ratings to measure fidelity.

(i) The PLOC will be used as the primary tailoring variable measure by all participants at 4 weeks following the start of the intervention (when condensed group or online programming is completed). The PLOC is a 22-item questionnaire that takes about 5 minutes. A link sent to each parent's email address will provide access to the questionnaire. The results of this questionnaire will determine responder status for each individual. If a parent scores below the cut-score

threshold on the PLOC or does not complete the PLOC, that family will be re-randomized to the second stage ADAPT interventions.

(ii) Context measures:

- (a) Demographic information such as gender, age, racial, and ethnic identity for parent and child;
- (b) employment;
- (c) income,
- (d) date/s and number of deployments for parents. Number and length of deployments will be assessed from 3 open-ended questions to obtain information about the extent of respondents' deployment history. Combat exposure will be measured using subscales from the DRRI, an ecologically valid instrument for assessing risk and resilience factors among military personnel participating in recent and current deployments.

(iii) Parenting practice measures:

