9.0 Study Population

9.1 Inclusion Criteria:

Recruitment is limited to families meeting the following inclusion criteria: (a) one parent has returned from deployment (b) at least one child age 5 to 12 in their custody and living with parent(s) in the home. (c) We will include both single- and two-parent families, as well as families where care is shared between non-partnered adults (e.g. grandparent and mother), and will control for relationship status in the analyses. (d) Participants must agree to randomization, and (e) indicate willingness to interact with study materials and complete assessment

batteries. Women and minorities are included in the study. Inclusion criteria (a), (b), (c), (d), and (e) are necessary to meet the specific aims of the study and to meet the requirements of PMTO/ADAPT.

9.2 Exclusion Criteria:

Exclusion criteria include: (a) families with children younger than 5 or older than 12 – see the above rationale for the age limitation of children; (b) parent has an active psychosis, (c) an open child protection case for abuse or neglect in the family, (d) a serious child mental health diagnosis, i.e., autism, child psychosis (e) youth do not meet age criteria, (f) youth have a documented pervasive developmental disability or mental retardation, (g) less than a 5th grade comprehension level in English. Children and families will not benefit from a prevention intervention if either the parent or the child has a serious mental illness, if the family has an active child protection case, or if the parents are not able to comprehend the materials.

Screening:

Potential participants will be asked to take an online eligibility survey that will screen for inclusion criteria.

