Off-duty and civilian parents will be paid \$25 for each online assessment (up to 2 parents/caregivers per family); \$50.00 for each in-home assessment/family (50);

\$100.00 for the final in-home / family; \$10.00/parent for the PLOC; \$25.00/parent at 6 month follow-up online only; \$25.00/parent at 12 month and 24 month follow-ups; \$25.00.

II. Incentives for Participation in the Interventions:

- (a) Self-directed online only: \$50.00/family
- (b) Condensed ADAPT: \$50.00/family
- (c) Full group ADAPT: \$50.00/family
- (d) Individual ADAPT: \$50.00/family

We will also provide small incentives for home practice assignment and group attendance via a drawing for snow scrapers, candles, etc.

Self-directed online only participants will have a chance to enter into a drawing based on the number of times (up to 7) that they respond to facilitator questions. One winner will be selected per cohort to receive a \$100 gift card.

III. Incentives for Children Participants:

Children will be given a gift worth approximately \$5.00 at Times 1, 3, and 4 for participating in the observation (FIT). Families are eligible to receive up to \$520.00 in total incentives.

IV. Incentives for Teacher Participants:

Teachers will be paid \$10.00 for completing assessments at Times 1, 3, and 4.

V. Incentives for Focus group Participants

- (a) Focus group participants will be paid \$25.00 per feedback session.

NOTE: Active duty participants are not allowed to receive incentives per DoD policy.

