The assessment package includes self-report measures (Table 1) to be completed by each participating parent or caregiver. The assessment package takes each adult approximately 35 minutes to complete, and upon completion participants are each compensated \$25 (per assessment package completed; up to two per family). Parents also are asked to schedule a 15-minute study orientation call, and in-home assessment appointment with project staff. Families who do not complete the online assessment will be asked to complete the assessment during the assessment in-home visit.

(6). A copy of the parental consent form will be offered to and left with families at the first (BL) in-home visit and all subsequent visits (T3 and T4).

(7). Child assent will be completed at the first (BL) in-home assessment. The assent form is attached.

a. In-home assessments will be conducted by pairs of well-trained research assistants located on or near each base who will be employees of the University of Minnesota with extensive experience with military families (as veterans, spouses or relatives, and/or service providers) and with some research experience. They will be provided extensive training in data privacy, HIPAA, human subjects' protection, the consent process, and assessments.

Note: childcare provided by study staff is offered during in-home assessments for siblings. If study staff are not available to provide childcare, a \$30 gift card stipend will be offered to the family so that they can arrange their own childcare.

b. Families who prefer assessment outside the home may go to the local project office. Following the BL assessment, participants are electronically (via computer program) given random assignment to clinical trial conditions, which have been explained during the consent process.

c. Teachers will be contacted via secure, encrypted email, with an explanation of the study, and a copy of the parent's release of information (see attached) . They will be directed to the study website to complete questionnaires. Teachers not

responding will receive materials by mail, with follow-up calls (this has been a very effective strategy in our prior studies).

22.2 Waiver or Alteration of Consent Process (when consent will not be obtained, required information will not be disclosed, or the research involves deception):

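### Standard ANCOVA for the Q2a and Q2b main effects makes no provision for two parents in one family, who share an arm; standard errors would be too small if both parents enter as rows

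*Combined protocol and SAP*

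**What the plan says.** **Unit counted and assigned.** Section 5.1 sets the sample as "Among 210 SO and 315 RA families (i.e., total N=525 families) with 5-12 year-old children". The table in 17.2 takes 10% off 525 to get 473 for Q2a, and 10% off 262 to get 236 for Q2b. These are counts of families. At the second stage, section 5.2 says "that family will be re-randomized to the second stage ADAPT interventions". The first stage is worded less exactly in 22.1: "Following the BL assessment, participants are electronically (via computer program) given random assignment to clinical trial conditions". Family-level assignment there is implied, because the programs in 5.2 are delivered to families.

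**Unit measured.** Section 9.1 states: "We will include both single- and two-parent families, as well as families where care is shared between non-partnered adults". The online package in 22.1 consists of "self-report measures (Table 1) to be completed by each participating parent or caregiver", and 12.5 pays for online assessments for "up to 2 parents/caregivers per family". Section 18.1 gives each person an individual number within a family number. One target child per family is selected (5.2).

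**Model.** Section 17.1 plans "standard normal theory Analysis of Covariance factorial and fractional factorial analyses to address study aims using pre-post assessment scores for parent and child adjustment constructs". It then brings in linear mixed models and weighted least squares for non-independence, but only for the embedded adaptive strategies. It does not define the ANCOVA row, say how two parents' scores are combined or separated, or name a family effect for Q2a or Q2b.

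**The concern.** Standard ANCOVA treats every row as independent. Two parents in one home live with the same child, share stressors and receive the same program, so their scores are likely to be positively correlated even after baseline adjustment. Since both are in the same arm, that correlation adds to the variance of the arm difference. An analysis with parents as rows and no family term leaves this out.

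The outcomes exposed are those that two parents can each report. From the online package, examples are depression symptoms (CESD), couple adjustment (DAS-7) and emotion regulation (DERS). At stake are confidence intervals that are too narrow and a false positive rate above nominal in the two main-effect questions. Because the row is undefined, several analyses of the same outcome also stay open after the data are seen.

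This layer is separate from clustering by workshop, booster group or facilitator. A term for any of those would not remove parent-within-family correlation.

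**Working it through.** **1. The plan's own figures.** For two equal arms, the minimal detectable effect is MDE = 2(z_α + z_power)/√N, with z_power = 0.842 for power .80.

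| | N (10% attrition) | two-sided α = .05 | two-sided α = .10 | stated in 17.2 |
|---|---|---|---|---|
| Q2a | 473 | .258 | .229 | .324 |
| Q2b | 236 | .365 | .324 | .458 |

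The stated values are not reproduced at either alpha that 17.2 names. They are matched at α = .10 with N halved (.3235 and .4578), a factor that the plan does not explain. That is a separate matter. What counts here is that N is the number of families, so the table counts each family once.

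**2. Inputs.** The documents give 473 and 236 families and at most two parents per family. They give neither the share q of two-parent families nor the correlation ρ between two parents' baseline-adjusted residuals. Both are assumed: q = .75 and ρ = .2 to .4 as the central case, with wider values in step 4.

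**3. If both parents are rows.** With family sizes of 1 and 2, the variance of an arm mean is inflated by

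DEFF = 1 + ρ × 2q/(1 + q).

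At q = .75, 2q/(1 + q) = 1.5/1.75 = .857, and there are 473 × 1.75 ≈ 828 rows for Q2a.

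- ρ = .2: DEFF = 1 + .2 × .857 = 1.171. Naive variance too small by 1 − 1/1.171 = 14.6%; standard error by 1 − 1/√1.171 = 7.6%.
- ρ = .4: DEFF = 1 + .4 × .857 = 1.343. Naive variance too small by 25.5%; standard error by 13.7%.

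The actual type I error is 2[1 − Φ(z/√DEFF)]:

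- nominal 5%: 1.96/√1.171 = 1.81 gives 7.0%; 1.96/√1.343 = 1.69 gives 9.1%.
- nominal 10%: 12.9% and 15.6%.

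**4. Range.** Over q = .5 to 1 and ρ = .1 to .5, DEFF runs from 1.067 to 1.5. The naive standard error is 3% to 18% too small, and nominal 5% becomes 5.8% to 11.0%. A simulation of 472 two-parent families (2,000 runs, ρ = .3) gave 8.9% for parent rows, against 8.6% from the formula, and 4.6% for family means.

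**5. If each family gives one row.** DEFF = 1 and the test is valid. The cost shows in precision. Take q = 1, ρ = .3, α = .05: a correctly clustered two-parent analysis has effective N = 946/1.3 = 728. The MDE is .208 for Q2a and .294 for Q2b, against .258 and .365 when each family contributes one parent's score. At q = .75 and ρ = .2 to .4, the clustered Q2a effective N is 828/1.171 ≈ 707 to 828/1.343 ≈ 616, and the MDE is .211 to .226.

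**The case against.** The strongest reply is that the plan never says both parents are rows. Its N equals families, 17.1 puts a data-reduction step before the ANCOVA, and it speaks of constructs, so family-level scores or separate mother and father models fit the text. Under either, there is no inflation. This stands, and it makes the size conditional. It does not supply the missing rule: data reduction is mentioned next to psychometrics with no word on combining parents, and mothers and fathers are separated only for satisfaction reporting. The relationship-status covariate in 9.1 adjusts the mean, not the within-family correlation.

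Family means deserve a fair hearing. If every family had two parents, averaging would keep the precision of the clustered model: the variance of a mean is (1 + .3)/2 = .65, and 473/.65 = 728. With single- and two-parent families mixed, however, averages and single scores have unequal variance, and caregiver role is lost.

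Some further readings are tempting but unsupported:

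- *Two-parent families are planned to count twice.* No section says so. Even if both parents were rows, the extra weight would change whom the average describes; it would not bias a randomized comparison.
- *All parent measures come from both parents.* The each-parent wording in 22.1 covers the online package. The appendix lists PCL, APQ-22 and BASC-3 as in-home, and 12.5 pays for in-home visits per family, so two reports on these are an inference. AUDIT is barred for active-duty participants and would usually have one respondent.
- *The power table is optimistic.* It counts families once, and a clustered two-parent analysis has a smaller MDE than one parent per family or the stated values.

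**Conclusion.** The point holds in conditional form. For Q2a and Q2b, 17.1 names an independence-based model for data that can contain two correlated parents in the same arm, and its only non-independence remedy lies elsewhere. If both parents are rows, and assuming residual correlation .2 to .4 with 75% two-parent families, true variance exceeds naive variance by 17% to 34% (equivalently, naive variance is 15% to 26% too small). A nominal 5% test then runs at about 7% to 9%. If one parent's score stands for each family, the test is valid but loses precision.

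A reader might infer that the main-effect standard errors are already wrong as planned; the documents do not settle the row, so they do not support that. Child self-report and teacher report on the single target child are not affected. Both q and ρ are assumptions, and first-stage assignment by family is implied rather than stated. The change should be made, because the named model can be replaced by one that is valid with both parents included and uses all the data.

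**What to change.** In 17.1, for every Q2a and Q2b outcome that two parents report, replace standard ANCOVA with a linear mixed model. Fixed effects: arm, baseline score and caregiver role; random effect: family intercept. ANCOVA with family-clustered robust variance is an acceptable alternative. Define role categories that also cover non-partnered caregivers (9.1 gives a grandparent and mother as an example) and couples who both serve. State which instruments each parent completes, and keep ordinary ANCOVA for outcomes with one report per family. A separate effect for the service member is optional. Family means or separate mother and father models would also be valid if prespecified, at the price noted above.

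The cost is SAP wording; the family identifier in 18.1 already exists. The downside is that p-values will be slightly less favorable than under a naive ANCOVA on parent rows.
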